1.3 Data coordination committee

[name] at Yale University will lead the Data Coordination Committee consisting of the personnel from Sun Yat-Sen Memorial Hospital of Sun Yat-Sen University, including registering the trial at the Chinese Clinical Trial Registry (<http://www.chictr.org/cn/>) and ClinicalTrials.gov (<http://www.ClinicalTrials.gov>). The daily operation of the Data Coordination Center is fully executed by the personnel at Sun Yat-Sen Memorial Hospital.

1.6 Publication committee

Members of the publication committee include [name], [name].

2. Background

The deferment of childbirth has emerged as a significant concern in recent years. Over the past forty years, the prevalence of primiparity at age of 35 years or older increased by 9 times (1). Advanced maternal age (AMA), defined as pregnancy at 35 years or older, is commonly linked with reduced fecundity (2,3). AMA patients are more inclined to the use of assisted reproductive technology (ART), including in vitro fertilization (IVF) and intracytoplasmic sperm injection (ICSI) (4). Nonetheless, their pregnancy outcomes are typically less favorable compared to their younger counterparts, as aging adversely affects both oocyte quality and ovarian reserve (5).

Traditional Chinese Medicine (TCM) has been employed for over two millennia in the treatment of a myriad of conditions, including infertility (6). A representative formula for the treatment of infertility is the Zishen Yutai Pill (ZYP). ZYP is a patent Chinese medicine invented by [name] (7). Since its market debut in 1983, ZYP was renowned for its therapeutic effects on threatened miscarriage and recurrent miscarriage. ZYP is consisted of fifteen Chinese medicine, including Cuscutae Semen, Ginseng Radix et Rhizoma, Dipsaci Radix, Taxilli Herba, Eucommiae Cortex, Morindae Officinalis Radix, Cervi Cornu Degelatinatum, Codonopsis Radix, Atractylodis Macrocephalae Rhizoma, Asini Corii Colla, Lycii Fructus, Rehmanniae Radix Praeparata, Polygoni Multiflori Radix Praeparata, Artemisiae Argyi Folium, and Amomi Fructus (8).

In previous clinical practice, the administration of ZYP was observed to enhance the ovulation and pregnancy rate, while decrease the miscarriage rate among patients with polycystic ovary syndrome (PCOS) (9). Another clinical report had suggested that oral intake of ZYP around the luteal phase could significantly increase the embryo implantation rate (10). Our previous multicenter, placebo-controlled, randomized clinical trial had suggested that the intervention of ZYP among advanced maternal aged women could significantly increase the clinical pregnancy rate during ART.

However, this analysis constituted a post hoc subgroup analysis, lacking the statistical power to detect the between-group difference. Therefore, the design of the current

study aims to provide data regarding the efficacy and safety of ZYP in IVF/ICSI for the AMA patients.

3. Objectives

The present study aims to investigate the efficacy and safety of ZYP on live birth rates among AMA infertile women during IVF/ICSI-ET. The primary objective is to determine the difference of live birth rate between the ZYP and placebo group. The secondary outcomes will include counts and rates of oocytes/embryos (oocytes retrieved, 2 pro-nuclei zygotes, cleavage zygotes, available embryos, high-quality embryos), pregnancy outcomes (rates of biochemical pregnancy, implantation, clinical pregnancy and miscarriage), incidences of maternal, fetal and neonatal complications, and neonate information (newborn birthweight and length, congenital malformation).

4. Participants

4.1 Inclusion criteria

Participants who meet all of the following criteria will be included in this study.

- (1) Infertile women aged between 35 and 42 years old.
- (2) Intend to undergo IVF-ET (GnRH-a long protocol or GnRH-ant protocol).
- (3) $BMI < 28 \text{ kg/m}^2$.
- (4) Bilateral ovaries exist.
- (5) Patients who voluntarily sign the informed consent and agreed to be followed up as required by the study protocol.

4.2. Exclusion criteria

Participants who meet one of the following criteria will be excluded in this study.

- (1) Recurrent implantation failure (previous three times or more IVF/ICSI-ET failure).

- (2) Adenomyosis, the uterine cavity line constricted by uterine fibroids.
- (3) Untreated bilateral hydrosalpinx.
- (4) Endometrial diseases that have not been cured.
- (5) Known diseases that are not suitable for undergoing ART or at the present not suitable for pregnancy;
- (6) Recent therapy (within one month) for infertility with TCM.

4.3 Drop-out

Participants will dropout when:

- (1) subjects who have adverse events that cannot be tolerated.
- (2) Severe breach of the protocol.
- (3) Subjects who exit due to personal or unpredictable reasons (detailed information need to be recorded).
- (4) Subjects considered inappropriate to continue to participate in the study for other medical reasons.

5. Study design

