5.4 Intervention of study drug

Eligible subjects will be allocated to receive ZYP or the placebo 3 times daily, 5 g

each time on down-regulation day (GnRH-a long protocol) or day 19 to day 23 of previous menstrual cycle (GnRH-ant protocol). Study drug will be suspended during the 1st day to the 4th day of menstrual cycle. Continuation of the study intervention will be determined by the serum β -HCG pregnancy test carried out two weeks after embryo transfer. Intervention of study drug will be stopped if the pregnancy test is negative. For patients with positive results on the pregnancy test, the study medicine will be given until a confirmed clinical pregnancy (five weeks after ET).

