5.4.3 Adherence of study drug

Patients' adherence of study drug will be assessed. An actual dosage above 80% of required drug dosage will be considered consistent with protocol requirements.

In order to record and improve the adherence of study drug, a diary card will be used. The diary card includes information of participants, study drug dosage, date of drug administered. In addition, each participant will be assigned a clinical research coordinator to assure the adherence of study drug and carry out follow-up.

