6.1 General visit setting

Briefly, five visit points are scheduled for this study. Visit 1 will be the screening visit. Visit 2 will be performed on the day of Gn initiation. Visit 3 will be carried out on the day of ET. Visit 4 will be carried out two weeks after ET to confirm biochemical pregnancy. Visit 5 will be carried out five weeks after ET to confirm clinical pregnancy. Follow-up after delivery will be conducted through web or telephone contact to ascertain the live birth outcomes of participants (**Figure 1**).

[figure not shown]

Figure 1. Study flowchart. Gn, gonadotropin; hCG, human chorionic gonadotropin; ZYP, Zishen Yutai Pill.

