12.3 Type of analysis

We will utilize an intent-to-treat approach to examine differences in the live birth rates for the first embryo transfer cycle in the two treatment arms in the primary analysis by the Pearson χ^2 test. Safety parameters and secondary efficacy parameters, such as pregnancy rate, miscarriage rate and other rates, will be analyzed using the Pearson χ^2 test or Fisher exact test as appropriate. Secondary efficacy parameters, including the counts and rates of oocytes/embryos, will be analyzed using the Mann-Whitney U test.

For the primary and secondary outcomes, we will also perform analysis in the per-protocol set (PPS), excluding those who have major protocol deviation(s), cancel cycle or do not complete the pre-set minimum exposure dosage of the assigned study drug (at least 80% compliance), from the ITT population. Subgroup analysis will be conducted as stratified by age (35-37, 38-39, 40-42).

Prior to unblinding, missing value in the primary outcome (live birth) and secondary outcomes (biochemical pregnancy, clinical pregnancy) in the ITT analysis will be imputed as not having an event.

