13.3 Recording of adverse events

All adverse events will be observed during the clinical trial. The investigators will require the participants to reflect the change in patients' condition truthfully after using the drug and avoid suggestive questions. Adverse events and unexpected side effects (including symptoms, signs, and laboratory tests) will be observed while observing the curative effect. In order to determine whether adverse events are associated with the experimental drug, they will be recorded in the eCRF in detail, including the occurrence time, symptoms, signs, degrees, duration, laboratory examination indicators, treatment methods, procedures, results, follow-up time, and so on. Concomitant medication will be recorded in detail to analyze the correlation between adverse events and experimental drugs. In addition, the record will be signed and dated.

When adverse reactions occur, the investigator will take necessary measures, such as adjusting the dose, temporarily discontinuing the medication, and decide whether to terminate the trial or not. If a serious adverse event occurs, the unit undertaking the study must immediately take necessary treatment measures to ensure the subject's safety.

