13.4.2 Severity assessment

The level of adverse event response will be evaluated and reported as follows:

Mild: The participant can tolerate the event, and it does not affect the treatment. It need not take special actions and is not harmful to the participant.

Moderate: The participant is intolerant and requires withdrawal or special treatment, which has a direct impact on their health.

Severe: It is a life-threatening, fatal, or disabling event and requires withdrawal or emergency treatment immediately.

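### Does the undefined meaning of dropout in section 4.3, with missing live births scored as failures, undermine the primary comparison?

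*Combined protocol and SAP*

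**What the plan says.** Section 4.3 gives four reasons for dropping out: intolerable adverse events, severe breach of the protocol, personal or unpredictable reasons, and "Subjects considered inappropriate to continue to participate in the study for other medical reasons". It does not separate stopping the drug from leaving follow-up. Section 13.3 comes closer to that distinction, since its options after an adverse reaction include "temporarily discontinuing the medication, and decide whether to terminate the trial or not". Section 13.4.2 defines a moderate event partly by withdrawal: "The participant is intolerant and requires withdrawal or special treatment".

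Section 12.3 makes the primary analysis an intent-to-treat Pearson chi-square test of live birth. Before unblinding, missing live births "in the ITT analysis will be imputed as not having an event". The other analyses are age subgroups and a per-protocol set. The latter removes women with major deviations, cancelled cycles, or who "do not complete the pre-set minimum exposure dosage of the assigned study drug (at least 80% compliance), from the ITT population".

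On outcome collection, section 6.1 states: "Follow-up after delivery will be conducted through web or telephone contact to ascertain the live birth outcomes of participants". Section 5.4.3 adds that "each participant will be assigned a clinical research coordinator to assure the adherence of study drug and carry out follow-up". Section 5.2 discloses allocation once all live birth information is in, section 11 reserves nine months for tracing outcomes, and section 4.1 requires agreement to follow-up.

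**The concern.** Nothing in the available text says in so many words that a woman who drops out is still followed to delivery (the flowchart and consent form could not be seen). Read strictly, item (4) of section 4.3 takes her out of the study. With 12 centres, sites could read it differently.

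Scoring her as no event is right if she never reaches transfer. It can be wrong if she stops study drug but still has a transfer, or drops out after transfer. The second case is possible: under section 5.4 a woman with a positive test takes study drug until five weeks after transfer. Births missed in this way would count as failures. If one arm lost more of them, the ITT difference would be biased, in either direction. The per-protocol analysis would not show this, because it changes the population and leaves the value given to a missing outcome alone.

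**Working it through.** **Inputs from section 12.2:** live birth per transfer 0.42 (ZYP) and 0.33 (placebo); 80% power, alpha 0.05 (two-sided, section 12.1); dropout before transfer 15%; cancellation 23%; 733 randomised per arm.

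**Assumptions, because the documents give no figure:** dropout imbalance between arms, the share *c* of dropouts who still reach transfer, and dropout after transfer.

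**1. The plan's own figure.** n = [1.960·√(2·0.375·0.625) + 0.842·√(0.42·0.58 + 0.33·0.67)]² / 0.09² = 453.04, rounded up to 454. Then 454/0.62 = 732.3, rounded up to 733. Both reproduce.

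**2. ITT result expected if all 38% count as no event.** ZYP 0.42 × 0.62 = 0.2604; placebo 0.33 × 0.62 = 0.2046. That is 191 vs 150 births of 733: p = 0.011, power 71.6%. The fall from 80% comes from counting all randomised women, not from this point.

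**3. Live birth per woman who does not drop out.** Placebo 0.33 × 0.62/0.85 = 0.241; ZYP 0.42 × 0.62/0.85 = 0.306.

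**4. Dropout before transfer, no true effect.** False difference = imbalance × 0.241 × *c*. Type I error is for the pooled two-sided test, 733 per arm, centred on 0.2046.

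| Dropout by arm | c = 0.25 | c = 0.5 | c = 1 (limit) |
|---|---|---|---|
| 17.5% vs 12.5% | 0.30 points, 5.2% | 0.60 points, 5.9% | 1.20 points, 8.8% |
| 16% vs 14% | 0.12 points, 5.0% | 0.24 points, 5.1% | 0.48 points, 5.6% |

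With equal dropout it stays at 5.0%.

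**5. Dropout after transfer, no true effect.** False difference = imbalance × 0.62 × 0.33. Imbalances of 1, 2 and 3 points give 0.20, 0.41 and 0.61 points, and type I error of 5.1%, 5.4% and 6.0%.

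**6. Planned effect with unequal dropout.** Take 17.5% on placebo and 12.5% on ZYP. Observed births are 733 × 0.875 × 0.306 = 196.5 (ZYP) and 733 × 0.825 × 0.241 = 145.6 (placebo), p = 0.0017. Missed births, with no treatment effect in dropouts, are 733 × 0.125 × *c* × 0.241 and 733 × 0.175 × *c* × 0.241. Adding them back:

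| c | Added (ZYP, placebo) | p |
|---|---|---|
| 0.25 | 5.5, 7.7 | 0.003 |
| 0.5 | 11.0, 15.4 | 0.005 |
| 1 | 22.1, 30.9 | 0.013 |

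Significance is kept throughout. With the imbalance reversed, observed births are 733 × 0.825 × 0.306 = 185.3 vs 733 × 0.875 × 0.241 = 154.4, p = 0.056. Adding back gives p = 0.043, 0.033 and 0.019. In that direction the rule works against the drug.

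**7. Tipping point from 191 vs 150.** Nine more births on placebo alone give p = 0.0499; ten give p = 0.058. At 0.33 births per transfer, ten births are 10/0.33 ≈ 30 more placebo dropouts after transfer, or about 6.7% of 454. If ZYP also missed 20 births, placebo would need 28 (211 vs 178, p = 0.051).

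**8. Power if dropouts were followed, c = 0.25.** 70.4% if they carry no treatment effect and 74.0% if they keep it; 67.4% and 80.6% at c = 1. As planned: 71.6%.

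**The case for a change.** The strongest contrary case is that outcomes not collected may be lost for good, about 110 women per arm are expected to drop out (15% of 733), and ten births missed on placebo alone would reverse a result exactly as planned. If every dropout had the same chance of birth as other women (0.33 × 0.77 = 25.4%), losses of 10% vs 20% would raise type I error to about 22%. Ten births could also come from fewer than 30 women if the losses were in women already known to be pregnant, whose live birth rate exceeds 0.33; at the extreme, ten women (10/454 = 2.2% of transfers).

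The arithmetic stands, and so does the gap in wording. What is missing is any sign that such losses would occur. The 22% needs a 10-point imbalance and every dropout having an undiminished chance of birth. Yet section 12.2 defines its 15% as dropout before transfer and counts none of those women among the transfers. Assignment is double-blind, and section 13.1 lists only nausea, dry mouth and constipation for ZYP. The pregnant women are also the hardest to lose: section 6.6 has sites check contact details and intended delivery hospital once clinical pregnancy is confirmed.

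**Conclusion.** No change is called for. This is a gap in wording that investigators and analysts can fill sensibly from the rest of the plan. The imputation applies only to values that are missing, so a live birth that has been ascertained is analysed as observed. Women who breach the protocol or take too little drug leave only the per-protocol set. The follow-up provisions speak of participants without excepting those who stop treatment. The missing-value rule is set before unblinding, and the outcome is objective.

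On assumed imbalances of 1 to 5 points, excluding the limit where every dropout continues to transfer, type I error lies between 5.0% and 6.0%, and following the dropouts would leave power close to its planned level. All imbalances and continuation shares are assumptions, so the documents neither show a material bias nor rule one out. A count of imputed outcomes by arm and a tipping-point analysis would be reasonable reporting additions, but they would leave the primary result as it is. The conclusion would need another look if, when the data are in, many live births after transfer turned out to be missing and unevenly split between the arms.

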5.1 General design

It will be a multicenter, prospective, randomized (1:1 treatment ratio) clinical trial comparing the live birth rates in AMA women assigned to these treatment arms after a fresh ET in 1466 infertile patients undergoing IVF or ICSI. Patients will be randomized into either of two groups, receiving ZYP or the placebo during IVF/ICSI. All of the participants will receive standardized controlled ovarian hyperstimulation (COH) protocols, i.e., GnRH agonist (GnRH-a) long protocol or GnRH antagonist (GnRH-ant) protocol), as appropriate, and then undergo embryo transfer (ET).

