The number of oocytes retrieved will be defined as the total number of oocytes retrieved through ultrasound-guided transvaginal aspiration. The rate of oocytes retrieved will be defined as the number of retrieved oocytes divided by the number of follicles with a diameter ≥ 10 mm on the HCG injection day. Matured oocytes will be defined as those with pronuclei or polar bodies observed on Day 1 after oocyte retrieval in IVF patients, or as the number of MII oocytes on the day of oocyte retrieval in ICSI patients. Cleavage oocytes will be defined as the number of fertilized oocytes that undergo cleavage on Day 2 after oocyte retrieval. The rate of cleavage will be defined as the number of cleaved embryos divided by the number of fertilized oocytes (2PN + 1PN + multiple PN). Available embryos will be defined as the sum of the number of embryos transferred and the number of embryos frozen. The rate of available embryos will be defined as the number of available embryos divided by the number of cleaved oocytes. High-quality embryo will be defined according to the day of embryo transfer, following the Istanbul consensus and Gardner criteria, Day 2: 4 cells, cell fragments $<10\%$ and no multi-nucleus; Day 3: 8 cells, cell fragments $<10\%$, no multi-nucleus; Day 5: stage 4 blastocyst, grade A inner cell mass, grade A trophectoderm (12,13). The rate of high-quality embryos will be defined as the number of high-quality embryos divided by the number of available embryos.

Biochemical pregnancy will be defined as positive when β -HCG >50 IU/L. Implantation rate will be defined as the number of gestational sacs per the number of embryos transferred. Clinical pregnancy will be defined as the presence of intrauterine gestation sac with fetal motion under transvaginal ultrasonography. Miscarriage rate will be calculated among patients with biochemical pregnancies and patients with clinical pregnancies.

Incidence of maternal, fetal and neonatal adverse events were assessed, including moderate or severe OHSS, gestational diabetes mellitus (GDM), gestational

hypertension, postpartum hemorrhage, preterm delivery, congenital anomalies, puerperal infection, stillbirth, neonatal jaundice, neonatal infection, neonatal death, ectopic pregnancy, and low birth weight infant. The definitions of these safety indexes were shown in **Table 6**.

Table 6. Definitions of safety outcomes

Safety outcome	Definitions

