12.1 General statistical consideration

For continuous variables, the Kolmogorov-Smirnov test will be applied to evaluate the distribution. Variables with normal distribution will be presented as means and standard deviation (SD), and intergroup comparisons will be performed using the 2-tailed, student's t test. Variables with non-normal distribution will be presented as medians and interquartile ranges (IQR), and intergroup comparisons will be performed using the Mann-Whitney U test. Categorical variables will be summarized with frequencies and percentages and compared using chi-square test or Fisher exact test, as appropriate. All statistical analysis will be conducted with the use of the statistical package SPSS, version 19.0 (SPSS Inc). A two-sided P value of <0.05 will be considered as significantly different.

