12.2 Sample size estimation

In our previous clinical research, the live birth rate was 0.42 per embryo transfer in ZYP treated group and 0.33 per embryo transfer in placebo control group among AMA women. By assuming the same live birth rates, a sample size of 454 women in each group can provide a power of 80% at a significance level of 0.05. According to previous study, the dropout rate before ET was 15% and the cycle cancellation rate was 23% in AMA women. For this trial, a total rate of 38% (dropout and cancellation) is considered in the sample size calculation. Therefore, a total of 1466 participants

will be recruited in this study, 733 participants in each group.

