In this study, the GnRH-a long protocol and GnRH-ant protocol will be performed according to each patient's actual situation. The GnRH-ant protocol will be used to minimize the risk of OHSS. The initial dose will be determined according to the age, basal FSH level, basal AFC, weight, and previous situation promoting ovulation. The initiation dose and total Gn dose will be adjusted according to a combined consideration of age, weight, basal hormone levels, AFC and previous cycle response. In addition, in case of high ovarian response, the cycle will be canceled to avoid OHSS. If there are three or more fetuses, then a reduction will be performed to minimize the risks of multiple pregnancies. A responsible investigator or a resident doctor on 24 h call can be contacted at each site if any adverse event occurs during this study.

Every effort will be taken to avoid injury as a result of participation. If adverse events occur, active treatment will be provided. Furthermore, if a medical dispute is involved, it will be disposed of as a routine medical event.

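### The primary endpoint is tied to a fresh transfer in 5.1 and to the first transfer cycle in 12.3, and no section says how to count a woman whose first transfer is frozen

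*Combined protocol and SAP*

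**What the plan says.** Section 5.1 (General design) sets the comparison as "comparing the live birth rates in AMA women assigned to these treatment arms after a fresh ET". Section 12.3 (Type of analysis) takes an ITT approach to "differences in the live birth rates for the first embryo transfer cycle". Section 10 defines live birth by viability and a 28-week threshold. It gives no transfer type, denominator or time window.

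Other sections bear on which transfer counts:

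- Section 5.3.3 describes transfer only on day 3 to day 5 after retrieval, which is a fresh transfer.
- Section 6.1 has one transfer visit, then visits two and five weeks later. No visit is set for a frozen transfer.
- Section 10 counts available embryos as "the sum of the number of embryos transferred and the number of embryos frozen", and Table 7 in 13.1 lists freezing and thawing among the procedures. Section 13.1 also states that "in case of high ovarian response, the cycle will be canceled to avoid OHSS".
- Section 12.3 removes cancelled cycles from the ITT population to form the per-protocol set, so cancelled women belong to the ITT set. Its imputation rule makes a missing live birth a non-event. It does not address an observed birth from a later frozen transfer.

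**The concern.** The two descriptions give the same endpoint only if every woman's first transfer is fresh. Take a randomised woman whose cycle has no fresh transfer and who delivers after a later frozen one. Under 12.3 read literally, her first transfer cycle led to a live birth. Under 5.1 there was no fresh transfer for a birth to follow. Her outcome is observed, so the missing-data rule does not apply. Delivery follow-up is by web or telephone (6.1) and could well pick up such a birth.

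Whether a woman reaches a fresh transfer is settled after randomisation. Study drug starts before stimulation (5.4), and oocyte and embryo yields are secondary efficacy outcomes, so the plan itself allows that the drug may alter ovarian response. A counting rule that depends on such an event should be fixed in advance. Otherwise two analysts, each following the plan, could classify the same woman differently in the primary result.

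**Working it through.** **Inputs (12.1 and 12.2).** Per-transfer live birth rates: "the live birth rate was 0.42 per embryo transfer in ZYP treated group" and "0.33 per embryo transfer in placebo control group among AMA" women. Size: "a sample size of 454 women in each group can provide a power of 80% at a significance level of 0.05". Test: "A two-sided P value of <0.05 will be considered as significantly different". Losses: 15% dropout before transfer plus 23% cancellation = 38%. Planned: 733 per arm, 1466 in total.

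**Formula.** Two proportions p1 and p0, mean m, difference d = p1 − p0, S0 = √(2m(1 − m)), S1 = √(p1(1 − p1) + p0(1 − p0)):

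- n per arm = ((1.96·S0 + 0.8416·S1)/d)²
- power = Φ((d√n − 1.96·S0)/S1)

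**Step 1: the plan's own figure.** With 0.42 and 0.33: m = 0.375, S0 = 0.6847, S1 = 0.6817, d = 0.09. This gives n = 453.04, rounded up to 454, with power 80.1% at 454. Inflation: 454/0.62 = 732.3, rounded up to 733 per arm. The stated size reproduces.

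**Step 2: fresh transfers only, all randomised women, the 38% counted as no live birth.**

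- ZYP: 0.62 × 0.42 = 26.0%
- Placebo: 0.62 × 0.33 = 20.5%
- d = 0.0558, S0 = 0.5974, S1 = 0.5961
- Power at 733 per arm: Φ(0.570) = 71.6%
- n for 80% power: 899 per arm

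This fall from 80.1% to 71.6% involves no frozen transfer. It comes from sizing on per-transfer rates and analysing by ITT.

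**Step 3: count a first frozen transfer as well.** Let f be the share of randomised women, equal in both arms, whose first transfer is frozen. The documents do not give f. I take 0 to 23%; the upper end means that every cancelled woman later has a frozen transfer. Two assumptions bound the effect in those transfers:

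- (a) full effect, rates (0.62 + f) × 0.42 and (0.62 + f) × 0.33
- (b) no effect, rates 0.62 × 0.42 + f × 0.33 and 0.62 × 0.33 + f × 0.33

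| f (assumed) | (a) rates | (a) power | (b) rates | (b) power |
|---|---|---|---|---|
| 0 | 26.0% v 20.5% | 71.6% | 26.0% v 20.5% | 71.6% |
| 5% | 28.1% v 22.1% | 75.9% | 27.7% v 22.1% | 69.5% |
| 10% | 30.2% v 23.8% | 79.9% | 29.3% v 23.8% | 67.7% |
| 15% | 32.3% v 25.4% | 83.4% | 31.0% v 25.4% | 66.1% |
| 23% | 35.7% v 28.1% | 88.2% | 33.6% v 28.1% | 63.8% |

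Under (a) the difference grows with f. Under (b) it stays at 5.6 points while the variance rises, so power falls.

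**The case against.** The best defence is that the plan has one endpoint, loosely worded. Transfer is described only on day 3 to day 5 after retrieval. No frozen-transfer visit exists. Dosing ends with the pregnancy test or five weeks after transfer, and the timeline allows about 3 months of treatment plus 9 of follow-up. All of this fits a fresh transfer. Frozen embryos may simply be surplus ones, the rule on high response speaks of cancelling and not of a later transfer, and 12.2 treats cancellation as a loss. This stands as the more natural reading. It does not supply the missing rule, because no section says that the first transfer means the fresh one, and cancelled women remain in the ITT set.

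A reader might infer more than the documents support:

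- **That the plan defines two conflicting endpoints.** The sections above allow one reading. Section 5.1 also gives no denominator, so it does not itself say that a woman without a fresh transfer is a non-event.
- **That counting frozen transfers raises power.** That needs the drug effect to carry over to them. Without carry-over, power falls.
- **That the difference between 5.1 and 12.3 decides whether 80% power holds.** The drop to about 72% arises from the per-transfer basis of 12.2 and is present at f = 0.
- **That the endpoint will be picked to suit the result.** Section 5.2 keeps blinding until the analysis is complete, which limits this. The same section has the system disclose allocation once all live birth data are in, so it is still safer to have the rule written beforehand.

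**Conclusion.** The primary endpoint is worded in two ways, and one class of women has no counting rule. The fresh reading is the better supported, but it is not stated. The size of the ambiguity cannot be fixed from the documents: it is nil if no first transfer is frozen. With an assumed share of up to 23%, equal in both arms, it spans about 64% to 88% power, in either direction.

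The separate mismatch between 12.2 and 12.3 is firmer. On the plan's own rates, with all of the 38% counted as no live birth, the primary ITT comparison at 733 per arm has about 72% power. It is best settled together with the definition, since power can only be restated once the endpoint is fixed.

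**What to change.** Before unblinding, put one definition in 5.1, 10 and 12.3: live birth from the fresh transfer of the randomised stimulation cycle, per randomised woman, with any woman who has no fresh transfer, for whatever reason, counted as having no live birth. This matches 5.1, the transfer timing, the dosing period and the follow-up timeline.

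Name live birth after the first transfer, fresh or frozen, as a sensitivity analysis, with a stated time window for the frozen transfer. Report by arm how many women had no fresh transfer and how many of those had a frozen first transfer.

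Restate power in 12.2 on the ITT definition: about 72% under the plan's assumptions.

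The cost is wording in the protocol and SAP, one extra analysis and a less favourable stated power. It changes no treatment.
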